## 4.5. Subject Withdrawal and Replacement

A subject is free to withdraw from the study at any time. In addition, a subject will be withdrawn from dosing if any of the following criteria are met:

- change in compliance with any inclusion/exclusion criterion that is clinically relevant and affects subject safety as determined by the Investigator (or designee)
- noncompliance with the study restrictions that might affect subject safety or study assessments/objectives, as considered applicable by the Investigator (or designee)
- occurrence of any Common Terminology Criteria for Adverse Events (CTCAE) v5 Grade ≥3 AE

- occurrence of Grade 2 AE considered by the Investigator (or designee) to be at least possibly related to sotorasib and, in the opinion of the Investigator (or designee), warrants subject withdrawal (e.g., neuropathy, chronic diarrhea, etc.)
- any clinically relevant sign or symptom that, in the opinion of the Investigator (or designee), warrants subject withdrawal.

If two or more subjects are withdrawn from the study due to AEs that are considered by the Investigator to be at least possibly related to sotorasib or if there is one Grade 3 event, dosing would be paused, and the Investigator and Sponsor will convene to review the data and determine the next step.

If a subject is withdrawn from dosing, the Sponsor (or designee) will be notified and the date and reason(s) for the withdrawal will be documented in the subject's electronic Case Report Form (eCRF). If a subject is withdrawn, efforts will be made to perform all EOS assessments, if possible (Appendix 9). Other procedures may be performed at the Investigator's (or designee's) and/or Sponsor's discretion. If the subject is inhouse-, these procedures should be performed before the subject is discharged from the clinic. The Investigator (or designee) may also request that the subject return for an additional follow-up visit. All withdrawn subjects will be followed until resolution of all their adverse events and serious adverse events, or until the unresolved adverse events and serious adverse events are judged by the Investigator (or designee) to have stabilized.

Subjects who are withdrawn for reasons not related to study drug may be replaced following discussion between the Investigator and the Sponsor. Subjects withdrawn as a result of adverse events/serious adverse events thought to be related to the study drug will generally not be replaced.

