# 4.6. Study Termination

The Sponsor may stop the study or study site participation in the study for medical, safety, regulatory, administrative, or other reasons consistent with applicable laws, regulations, and Good Clinical Practice. Both the Sponsor and the Investigator reserve the right to terminate the Investigator's participation in the study according to the Clinical Trial Agreement. The Investigator is to notify the Institutional Review Board (IRB) in writing of the study's completion or early termination and send a copy of the notification to the Sponsor. The Sponsor reserves the unilateral right, at its sole discretion, to determine whether to supply investigational product and by what mechanism, after termination of the study.

In addition, the study may be terminated by the Sponsor at any time and for any reason. If the Sponsor decides to terminate the study, they will inform the Investigator as soon as possible.

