# Serious Adverse Events

The Investigator is responsible for ensuring that all serious adverse events observed by the Investigator or reported by the subject that occur after signing of the ICF through 30 days after the last dose of study treatment or the EOS visit (whichever is later) are reported using the

appropriate eCRF and reported on the paper-based Serious Adverse Event Report Form (described in Appendix 1).

All serious adverse events will be collected, recorded, and reported to the Sponsor within 24 hours of the Investigator's knowledge of the event. The Investigator will submit any updated serious adverse event data to the Sponsor within 24 hours of it being available.

The criteria for grade 4 in the Common Terminology Criteria for Adverse Events grading scale differs from the regulatory criteria for serious adverse events. It is left to the Investigator's judgment to report these grade 4 abnormalities as serious adverse events.

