#### **Results in death (fatal)**

#### **Immediately life-threatening**

The term "life-threatening" in the definition of "serious" refers to an event in which the subject was at risk of death at the time of the event. It does not refer to an event, which hypothetically might have caused death, if it were more severe. For instance, drug-induced hepatitis that resolved without evidence of hepatic failure would not be considered life-threatening even though drug-induced hepatitis can be fatal.

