# Table 3:Conditions for Withholding and/or Permanent Discontinuation of Amgen
Investigational Product and Other Protocol-required Therapies Due to
Potential Hepatotoxicity

Analyte	Temporary Withholding	Permanent Discontinuation
TBL	>3x ULN at any time	>2x ULN
INR		>1.5x (for subjects not on anticoagulation therapy)
	OR	AND
AST/ALT	>8x ULN at any time	In the presence of no important alternative
	>5x ULN but <8x ULN for $\geq$ 2 weeks	causes for elevated AST/ALT and/or TBL
	>5x ULN but <8x ULN and unable to adhere to enhanced monitoring schedule	values
		>3x ULN (when baseline
	>3x ULN with clinical signs or symptoms that are consistent with hepatitis (such as right upper quadrant pain/tenderness, fever, nausea, vomiting, and jaundice)	was < ULN)
	OR	
ALP	>8x ULN at any time	

Abbreviations: ALP = alkaline phosphatase; ALT = alanine aminotransferase; AST = aspartate aminotransferase; INR = international normalized ratio; TBL = total bilirubin; ULN = upper limit of normal.

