## The primary changes in this amendment, along with the rationale for the/each change as appropriate, are:

- 1. Based on recommendations from the regulatory agency, the protocol was modified to add additional criteria for subject withdrawal from the study and criteria for pausing dosing.
- 2. Based on recommendations from the regulatory agency, the protocol was modified to add additional follow-up laboratory evaluations for subjects who develop clinically meaningful abnormalities outside the reference range during the study period.

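### The dosing pause is triggered by one Grade 3 event while withdrawal uses Grade 3 or higher; a lesser point is that the permanent liver stop omits subjects enrolled at or above ULN

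*Protocol*

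**What the plan says.** Protocol Section 4.5 holds both the individual and the study-level rule. One ground for withdrawing a subject from dosing is "occurrence of any Common Terminology Criteria for Adverse Events (CTCAE) v5 Grade ≥3 AE", with no condition on cause. The study-level pause has two triggers. The first opens "If two or more subjects are withdrawn from the study due to AEs" and counts only events that the investigator considers at least possibly related to sotorasib. The second is "or if there is one Grade 3 event, dosing would be paused", after which the investigator and sponsor review the data. Amendment 2 introduced these rules on a regulatory agency's recommendation; in its words, "the protocol was modified to add additional criteria for subject withdrawal from the study and criteria for pausing dosing".

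Appendix 7, Table 3, gives the liver rules. Where no important alternative cause exists, permanent discontinuation needs TBL above 2x ULN or INR above 1.5, together with an AST/ALT limb that begins ">3x ULN (when baseline" and continues with a baseline below ULN. The table shows no limb for any other baseline. The temporary-withholding column carries no baseline condition. The rechallenge section of Appendix 7 bars rechallenge absolutely only for subjects who meet the permanent criteria.

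Exclusion criterion 11 (Section 4.2) asks for ALT and AST below ULN at Screening. On a repeat test, however, it allows enrolment at ULN, or above ULN if the investigator judges the value not clinically significant, with 1.5x ULN as the example.

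**The concern.** A rule that halts dosing across a multi-center study should be at least as sensitive to the gravest events as to the less grave. Here the individual rule covers Grade 3 and everything above it, while the pause rule names Grade 3 alone. At stake is whether other healthy volunteers go on being dosed, without a required review, after one subject has a life-threatening or fatal event.

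The liver table raises a similar question on a smaller scale. Eligibility and stopping rule do not cover the same people: a subject can be enrolled at a baseline for which the permanent stop is not defined. Increased liver enzymes are a listed adverse reaction to sotorasib (Section 1.4.1.2), and liver monitoring is the stated mitigation.

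**Working it through.** **Pause rule.** All inputs are in Section 4.5. Applied as written to a single event in a single subject:

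| Event grade | Meets withdrawal rule (Grade 3 or higher) | Meets Grade 3 clause | Related withdrawals (2 needed) | Pause mandated |
|---|---|---|---|---|
| 3 | yes | yes | at most 1 | yes |
| 4 | yes | no | at most 1 | no |
| 5 | yes | no | at most 1 | no |

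One subject contributes one withdrawal to the count if the event is possibly related, and none if it is not. Since 1 < 2, the other trigger cannot fill the gap.

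**Liver rule.** Values are multiples of ULN, except INR.

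- Permanent stop: (TBL > 2 or INR > 1.5) and AST/ALT > 3 and baseline < 1. The table as read shows no connector between TBL and INR; *or* follows the later part of Appendix 7, which treats either elevation as sufficient for daily retesting.
- Temporary withholding: TBL > 3; or AST/ALT > 8; or AST/ALT between 5 and 8 for at least 2 weeks, or with enhanced monitoring not possible; or AST/ALT > 3 with signs or symptoms of hepatitis; or ALP > 8.
- Held fixed: no alternative cause, no symptoms, ALP at most 8, monitoring feasible. The 2-week condition cannot be met while doses remain, because Day 7 − Day 1 = 6 days, against 14.

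Take ALT 7 with TBL 2.5. No temporary criterion applies: 2.5 is not above 3, 7 is not above 8, and the conditions attached to the 5-to-8 range are not met. For the permanent stop, 2.5 > 2 and 7 > 3 both hold, so baseline decides:

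| Baseline (x ULN) | Baseline < 1 | Table 3 result | Rise over baseline |
|---|---|---|---|
| 0.9 | yes | permanent stop | 7/0.9 = 7.8-fold |
| 1.0 | no | neither column | 7/1.0 = 7.0-fold |
| 1.2 | no | neither column | 7/1.2 = 5.8-fold |
| 1.5 | no | neither column | 7/1.5 = 4.7-fold |

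Scanning AST/ALT from 0 to 12 and TBL from 0 to 5 in steps of 0.1 gives the full region that is a permanent stop below ULN but in neither column at or above it. AST/ALT is above 3 and up to 8, with either TBL above 2 and up to 3, or INR above 1.5 (1.6 in the scan) and TBL up to 3. Appendix 2 has INR tested only when hepatotoxicity is suspected, so the INR route describes someone already under scrutiny.

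**How many doses this can change.** The schedule in Appendix 9 puts on-treatment safety laboratory tests on Days 3 and 6 and doses on Days 1, 4 and 7. A Table 3 decision can therefore alter the Day 4 dose for most subjects, and the Day 4 and Day 7 doses for 14 of about 146 (14/146 = 9.6%). After the last dose nothing is left to discontinue.

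**The case against.** On the pause rule, the best defence is that no sensible reader would pause for Grade 3 and carry on after Grade 4 or a death. The withdrawal criterion in the same section says Grade 3 or higher. A fatal or immediately life-threatening event is serious under Appendix 1 and goes to the sponsor within 24 hours. The sponsor is also told of every withdrawal from dosing, and under Section 4.6 "the study may be terminated by the Sponsor at any time and for any reason". A reader might infer that the plan would let dosing continue after a death; given these provisions, the documents do not support that. What they provide, though, is notice and discretion rather than a required pause. For Grade 4 abnormalities, Section 7.2.1 leaves even serious-event reporting to the investigator's "judgment to report these grade 4 abnormalities as serious adverse events". A reader might also infer that the regulator's request was not met, but the documents do not give the agency's wording.

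On the liver rule, a reader might infer that subjects with a raised baseline are left unmanaged. They are not. Temporary withholding applies at any baseline. In the worked example, Appendix 7 requires close observation, repeat tests within 24 hours and, with TBL above 2x ULN, retesting every 24 hours until improvement. It also names elevated baselines expressly, through a 2-fold rise. Withdrawal under Section 4.5 remains open. Rechallenge needs an alternative cause, resolution of the abnormalities and unanimous agreement. All of this stands and makes the consequence narrow. None of it supplies a permanent stop: observation is not discontinuation, and Section 4.5 depends on a recorded adverse event or on judgement. Finally, the table is broken by extraction, but the baseline phrase is complete and nothing suggests a lost row.

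**Conclusion.** The pause rule is incomplete as written and should be corrected. Its literal effect is that the two highest grades, occurring singly, carry no mandatory pause; its practical effect is limited, because the intent is very likely Grade 3 or higher. That intent is an inference from the withdrawal criterion, not something the protocol states.

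The liver mismatch is real but minor. It needs a subject enrolled at or above ULN, a combined rise inside the region above without symptoms or an alternative cause, and a dose still to come. That this group is small is an assumption, based on enrolment at or above ULN being an exception to the Screening default. The figure of 1.5x ULN is the protocol's example, not a cap.

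Neither gap touches the sample size, the analysis or the bioequivalence conclusion.

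**What to change.** In Section 4.5, change the pause trigger from one Grade 3 event to one Grade ≥3 event. This is a wording correction with no new procedure.

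In Table 3, remove the baseline restriction, so that AST/ALT above 3x ULN with TBL above 2x ULN or INR above 1.5, and no important alternative cause, is a permanent stop at every baseline. The absolute bar on rechallenge then covers these subjects too. The small cost is that a subject enrolled at or above ULN would be stopped after a smaller relative rise: at the 3x limit, 3/1.0 = 3.0-fold from a baseline at ULN and 3/1.5 = 2.0-fold from 1.5x ULN, against more than 3-fold from any baseline below ULN. A multiple-of-baseline criterion would avoid that, but needs a clinical figure that the documents do not give.

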#### Criteria for Rechallenge of Amgen Investigational Product and Other Protocol-required Therapies After Potential Hepatotoxicity

The decision to rechallenge the subject is to be discussed and agreed upon unanimously by the subject, Investigator, and Amgen.

If signs or symptoms recur with rechallenge, then OM is to be permanently discontinued.

Subjects who clearly meet the criteria for permanent discontinuation (as described in Table 3) are never to be rechallenged.

## Drug-induced Liver Injury Reporting and Additional Assessments

#### Reporting

To facilitate appropriate monitoring for signals of DILI, cases of concurrent AST or ALT and TBL and/or INR elevation, according to the criteria specified above, require the following:

- The event is to be reported to Amgen as a serious adverse event within 24 hours of discovery or notification of the event (i.e., before additional etiologic investigations have been concluded).
- The appropriate electronic Case Report Form (eCRF) that captures information necessary to facilitate the evaluation of treatment-emergent liver abnormalities is to be completed and sent to Amgen.

Other events of hepatotoxicity and potential DILI are to be reported as serious adverse events if they meet the criteria for a serious adverse event defined in Appendix 1.

## Additional Clinical Assessments and Observation

All subjects in whom investigational product(s) or protocol-required therapies is/are withheld (either permanently or conditionally) due to potential DILI as specified in Table 3 or who experience AST or ALT elevations >3 x upper limit of normal (ULN) or 2-fold increases above baseline values for subjects with elevated values before drug are to undergo a period of "close observation" until abnormalities return to normal or to the subject's baseline levels.

Assessments that are to be performed during this period include:

- Repeat AST, ALT, ALP, bilirubin (BIL) (total and direct), and INR within 24 hours
- In cases of TBL >2x ULN or INR > 1.5, retesting of liver tests, BIL (total and direct) and INR is to be performed every 24 hours until laboratory abnormalities improve.

Testing frequency of the above laboratory tests may decrease if the abnormalities stabilize or the investigational product(s) or protocol-required therapies has/have been discontinued AND the subject is asymptomatic.

Initiate investigation of alternative causes for elevated AST or ALT and/or elevated TBL.

The following are to be considered depending on the clinical situation:

- Complete blood count with differential to assess for eosinophilia
- Serum total immunoglobulin (Ig)G, anti-nuclear antibody anti-smooth muscle antibody, and liver kidney microsomal antibody-1 to assess for autoimmune hepatitis
- Serum acetaminophen (paracetamol) levels
- A more detailed history of:

- $\circ$  Prior and/or concurrent disease or illness
- o Exposure to environmental and/or industrial chemical agents
- Symptoms (if applicable) including right upper quadrant pain, hypersensitivity-type reactions, fatigue, nausea, vomiting and fever
- o Prior and/or concurrent use of alcohol, recreational drugs, and special diets
- Concomitant use of medications (including nonprescription medicines and herbal and dietary supplements), plants, and mushrooms
- Viral serologies
- Creatine phosphokinase, haptoglobin, lactate dehydrogenase, and peripheral blood smear
- Appropriate liver imaging if clinically indicated
- Appropriate blood sampling for pharmacokinetic analysis, if this has not already been collected
- Hepatology consult (liver biopsy may be considered in consultation with a hepatologist).

Follow the subject and the laboratory tests (ALT, AST, TBL, INR) until all laboratory abnormalities return to baseline or normal or considered stable by the Investigator. The "close observation period" is to continue for a minimum of 4 weeks after discontinuation of all investigational product(s) and protocol-required therapies.

The potential DILI event and additional information such as medical history, concomitant medications, and laboratory results must be captured in the corresponding eCRFs.

#### **Appendix 8: Sample Subject Questionnaire**

#### Medicine Acceptability Questionnaire

#### (administered after each dose by Study Staff)

Please circle the regimen you just took: 8 X 120mg tablets 3 X 320mg tablets

1. How convenient is this medicine?

For each of the following statements, please tick the ONE box that best describes your opinion.

This medicine	Strongly disagree	Disagree	Neither agree nor disagree	Agree	Strongly agree
is a convenient amount for me to take. (E.g. number of tablets or volume of liquid.)					
is easy to fit into my lifestyle.					
is easy to take. (E.g. consider need for taking on an empty stomach or standing upright.)					
is suitable to take when not at home. (E.g. consider need for water, or ease of carrying.)					0

Please tell us overall how happy you are with the convenience of this medicine. Please CROSS the number that best describes how you feel (X).

#### 2. How does this medicine taste?

For each of the following statements, please tick the ONE box that best describes your opinion.

This medicine	Strongly disagree	Disagree	Neither agree nor disagree	Agree	Strongly agree
tastes good.					
has no aftertaste.					

Please tell us overall how happy you are with the taste and texture of this medicine. Please CROSS the number that best describes how you feel (X).

#### 3. How does this medicine look and how easy is the administration?

For each of the following statements, please tick the ONE box that best describes your opinion.

This medicine	Strongly disagree	Disagree	Neither agree nor disagree	Agree	Strongly agree
is the size easy to swallow.					
is the number of tablets easy to swallow.					
is easy to see.					
has a nice color.					

Please tell us overall how happy you are with the size and number of tablets of this medicine. Please CROSS the number that best describes how you feel (X).

#### 4. Overall acceptability based on convenience, taste and administration?

Please tell us overall how happy you are with the acceptability of this medicine. Please CROSS the number that best describes how you feel (X).

## **Appendix 9: Schedule of Assessment**

## Schedule of Assessments

	Screening	Check-in	Period 1			Period 2			Period 3		
Study Procedures	Day -28 to Day -2	Day -1	Day 1	Day 2	Day 3	Day 4	Day 5	Day 6	Day 7	Day 8	Day 6 or Day 9 (EOS/ ET)
Confined to the CRU		Х	Х	Х	Х	Х	Х	Х	Х	Х	X
Outpatient Visit	Х										
Inclusion/Exclusion Criteria	Х	Х									
Informed Consent	Х										
Demographics	Х										
Serology	Х										
Medical History	Х	Xa									
Height and BMI	Х										
Weight	Х	Х									X 
Drug Screen	Х	Х									
Alcohol Test	Х	Х									
Pregnancy Test (females only) b	Х	Х									$X^1$
FSH (postmenopausal females only)	Х										
12-lead Electrocardiogram c	Х	Х	Х			Х			Х		X 
Vital Signs d	Х	Х	Х	Х		Х	Х		Х	Х	X 
Clinical Laboratory Evaluations e	Х	Х			Х			Х			X 
eGFR f	Х	Х									
Physical Examination g		Х									$X^1$
Sotorasib Dose h			Х			Х			Х		
Subject Questionnaire			Х			Х					
Sotorasib PK Blood Samples i			Х	Х	Х	Х	Х	Х	Х	Х	Х
Adverse Event Monitoring j		X									
Serious Adverse Event Monitoring j	Х	Х									
Prior/Concomitant Medications k	X	X									

Abbreviations: BMI = body mass index; CRU = Clinical Research Unit; eGFR = estimated glomerular filtration rate; EOS = end of study; ET = early termination; FSH = follicle-stimulating hormone; PK = pharmacokinetic.

a Interim medical history only.

b Performed in serum at Screening and in urine at all other times. A positive urine pregnancy test will be confirmed with a serum pregnancy test.

## Protocol Amendment 2 Labcorp Drug Development Study: 8471128

c Electrocardiograms will be collected after the subject has rested in the supine position for at least 5 minutes, and will be obtained prior to the scheduled blood draws at: Screening; Check-in; prior to and 0.5, 2, and 4 hours following sotorasib administration on Days 1, 4 and 7; and EOS or ET. The 30-minute postdose ECG measurement will have a collection window of  $\pm$  2 minutes, the 2-hour postdose ECG measurement will have a collection window of  $\pm$  5 minutes, and the 4-hour postdose ECG measurement will have a collection window of  $\pm$  10 minutes.

d Vital signs measurements (supine blood pressure [BP], supine heart rate, respiratory rate, and oral body temperature) should be carried out prior to having blood drawn. Screening; Check-in; prior to sotorasib administration on Days 1, 4 and 7; 1 and 24 hours following sotorasib administration on Days 1, 4 and 7; and EOS/ET. Heart rate and BP will be measured using the same arm for each reading after the subject has been resting in the supine position for at least 5 minutes.

e Clinical chemistry (fasted at least 8 hours), hematology, and urinalysis.

- f eGFR will be calculated using the Modification of Diet in Renal Disease equation.
- g A full physical examination at Check-in and a symptom-directed physical examination at EOS/ET.

h Dose administration of sotorasib is to occur during the mornings of Days 1, 4 and 7 in accordance with the formulation of sotorasib administration specific to their treatment (Treatment A, Treatment B or Treatment C).

 Blood samples for determination of sotorasib plasma concentrations will be collected: Predose (Hour 0), 0.5, 1, 1.5, 2, 2.5, 3, 3.5, 4, 5, 6, 8, 10, 12, 24, 36, and 48 hours postdose following administration of sotorasib on Days 1, 4 and 7. The PK sample collected at 30 minutes postdose will have a sampling window of  $\pm 2$  minutes, samples collected from 1 through 3 hours postdose will have a sampling window of  $\pm 5$  minutes, samples collected from 4 through 10 hours postdose will have a sampling window of  $\pm 10$  minutes, and samples collected from 12 through 48 hours postdose will have a sampling window of  $\pm 20$  minutes. Times of all PK samples will be recorded to the nearest minute.

j Adverse events will be recorded from initiation of study treatment on Day 1 until EOS completion. Serious adverse events will be recorded from the time the subject signs the ICF through 30 days after the last dose of study treatment or the EOS (whichever is later).

k Prior and concomitant medication administration will be recorded beginning at informed consent. In addition, all Investigator-approved medications taken by a subject within 30 days or 5 half-lives (whichever is longer) prior to enrollment administration for over-the-counter or prescription medications, and 30 days prior to enrollment for herbal medicines (eg, St. John's wort), vitamins, and supplements, will be recorded on the subject's electronic Case Report Form.

Assessment to be performed at the EOS or if a subject is withdrawn early from the study.

